14.3.2 Criteria for Premature Study Discontinuation for an Individual Participant

The criteria for premature discontinuation from the study for an individual participant are:

- Lost to follow up as evidenced by failure by the participant to attend a safety visit after multiple attempts at rescheduling, at the discretion of the site investigator
- Request by participant to withdraw
- Request of the primary care provider if s/he thinks the study is no longer in the best interest of the participant
- Participant judged by the investigator to be at significant risk of failing to comply with the provisions of the protocol as to cause harm to self or seriously interfere with the validity of study results

14.4 **Toxicity Management**

In the event of noted side effects, treating physicians will provide whatever available treatment is considered best to protect patient safety and well-being; compliance with study requirements will not compromise such treatment. Guidelines for the management of known side effects of tesamorelin that do not require immediate discontinuation of study drug are as follows.

14.4.1 Elevated IGF-1: IGF-1 will be checked at each visit, and results will be reviewed by an independent endocrinologist at MGH who has the randomization code for both study sites. If a subject receiving tesamorelin has an IGF-1 z-score of ≥ 3 , the endocrinologist will contact the site investigator to recommend a dose-decrease of study drug to 1mg daily. If the subject is in the double-blind phase of treatment, the independent endocrinologist will simultaneously recommend a dose decrease for a placebo subject from the same site whose visit was temporally closest to the visit of the tesamorelin subject requiring dose reduction. Dose reductions should be enacted within 1 month of the IGF-1 level being drawn. Any dose reductions taking longer than this will be reported as protocol deviations. If a tesamorelin subject continues to have IGF-1 z-score ≥ 3 following dose reduction, the subject will be discontinued from the study.

14.4.2 Injection site reaction: A mild degree of non-pruritic swelling and mild erythema at the site of the injection that resolves within a few hours is relatively common with

tesamorelin and does not necessarily represent a hypersensitivity reaction. Subjects who present with this reaction will be asked to monitor for resolution and to let the study investigator know of any spread beyond the injection site or any pruritis, either of which may represent hypersensitivity. Erythema and pruritis extending >3cm beyond the injection site will be treated as a likely hypersensitivity reaction. If this is accompanied by any systemic symptoms such as shortness of breath or swelling suggestive of anaphylaxis, subjects will be discontinued from the study immediately and will be directed to immediate care. If the erythema and pruritis are not accompanied by any systemic symptoms, subjects will be asked to hold the study drug until resolution of the symptoms. At the study investigator's discretion, the subject may restart study drug once to determine if the reaction recurs. With recurrence, subjects will be discontinued from the study.

- 14.4.3 Joint pain: Joint pain of varying severity is a possible side effect of tesamorelin. For **mild joint pain**, subjects will be offered the choice of continuing the study drug or discontinuing the medication to see if the joint pain resolves. If joint pain resolves with discontinuation and thus is presumably related to tesamorelin, the subject may elect to discontinue or to continue in the study with careful monitoring as long as the joint pain is mild. Lack of resolution will prompt referral to the subject's usual care providers for further evaluation. For **moderate to severe** joint pain, i.e., pain that interferes with sleep or affects physical function, subjects will be asked to discontinue the study drug to determine if the joint pain resolves. If the joint pain resolves and thus is presumably related to tesamorelin, subjects will be discontinued. If joint pain does not resolve, subjects will continue to hold the study drug and will be referred to their usual care providers for evaluation. If an alternate etiology is found, subjects may elect to resume study drug.
- 14.4.4 Peripheral edema: Peripheral edema will be carefully assessed at baseline, as many subjects may have some degree of edema. If peripheral edema worsens during the study, subjects will be asked to have evaluation with their regular care provider for possible etiologies (cardiac, renal), with the understanding that an increase in edema may also be due to study drug. If no other etiology is found and if the edema does not interfere with physical function, the subject may continue in the study with careful monitoring if s/he wishes.
- 14.4.5 Hyperglycemia/glucose intolerance: Fasting glucose will be checked at every visit. For any fasting glucose of >150mg/dL, or >180 mg/dL for individuals with known type 2 diabetes at study entry, subjects will be contacted to arrange a re-draw. If fasting glucose persists >150mg/dL, or >180 mg/dL for individuals with known type 2 diabetes at study entry, subjects will be discontinued. Subjects without diabetes at study entry who develop fasting glucose >126mg/dL but <150mg/dL during the study, or any subjects who are found to have increases in HbA1c or adverse changes in glucose tolerance, will be reminded that tesamorelin may contribute to increased blood sugar and will receive additional counseling regarding limiting caloric intake. They will also be asked to discuss their glucose control with their regular care provider. Such subjects may continue in the study if they wish, with continued monitoring of glucose per protocol.
- 14.4.6 Malignancy: There is no evidence linking tesamorelin to the development of or worsening of malignancy. Nonetheless, there is theoretical concern that increasing growth hormone levels may promote tumor growth. Consequently, subjects with active malignancy will not be allowed in the study, and subjects with any new malignancy discovered during the study will be discontinued from the study.

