11. INTERVENTIONS

11.1 Biomedical Interventions (Study Drug)

11.1.1 Regimen

- Double blind phase (first 12 months): subjects will receive tesamorelin vs. identical placebo, formulated as described below, according to their randomization.
- Open label phase (last 6 months): subjects will receive tesamorelin, formulated as described below
- Tesamorelin and identical placebo will be provided by Theratechnologies, Inc. (Montreal, Canada). The dose of tesamorelin will be 2 mg SC QD, with provision for a dose adjustment to 1mg SC QD if subject's IGF-1 is ≥ 3 (see below and Section 14.4.1). All doses will be self-administered by the subject, after s/he receives instruction in reconstitution and administration and demonstrates competence in self-injection. Dosing is based on prior studies of this compound in HIV-infected patients with fat accumulation in which GHRH¹⁻⁴⁴ at 2mg significantly reduced visceral fat, improved lipid parameters, while achieving a generally physiologic increase in IGF-I of 80% vs. placebo over 6 months [54].
- Dose adjustment: If a subject who is receiving tesamorelin in either the double-blind phase or open-label phase has an IGF-1 z-score ≥ 3 , a dose reduction to 1mg will be performed. If the subject is in the double-blind phase, this will be accompanied by a dummy dose reduction for a placebo subject in order to maintain blinding, as described in 14.4.1. If the subject's next IGF-1 level shows z-score ≥ 3 , s/he will be discontinued from the study. If the next IGF-1 z-score is < 3 , the subject will continue in the study at

the 1mg dose. Dose reductions will remain in place for the remainder of the subject's participation in the study.

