12.4.4 Follow-Up: Please see description of follow-up visits in section 12.1

12.4.5 Early Termination Visit: Subjects who end the study early will be asked come for a study termination visit (please see Appendix A).

12.4.6 Pregnancy Visit: Every effort will be made, both through absolute eligibility criteria and ongoing counseling about contraception and risk for participating women of child-bearing age, to prevent pregnancy during the study. Should pregnancy occur, a participant would be asked to discontinue the medication immediately and to come for a visit in order to discuss the situation with the Site PI. Such participants would also be asked to remain in contact with the PI and study team through the completion of the pregnancy in order to document the outcome.

12.4.7 Other Visits: Aside from the visits described in this section and in 12.1, no other visits are anticipated.

12.4.8 Final Study Visit: Please see description of 18 month visit above. Subjects who leave the study early will be asked to come for an early termination visit in lieu of their next scheduled study visit as discussed above.

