14.2 Pregnancy

Women able to bear children will be repeatedly counseled about the risks of pregnancy during the study and the importance of contraception, and women will be instructed to immediately discontinue the study drug if they suspect pregnancy. If a participant becomes pregnant during the study, she will

- Discontinue the study agent
- Withdraw from the study but continue in follow-up for safety
- Be advised to notify her obstetrician of study agent exposure

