14.3 Criteria for Discontinuation

14.3.1 Criteria for Permanent Intervention Discontinuation for an Individual Participant

The criteria for permanent discontinuation of further study intervention for an individual participant are

- Fasting glucose >150mg/dL, or >180 mg/dL for individuals with known type 2 diabetes at study entry, at any visit, confirmed by re-draw
- Erythema and/or pruritis extending ≥ 3 cm beyond the immediate injection site, indicating allergic reaction
- Pregnancy
- Active malignancy
- Evolving medical condition (e.g., progressive liver disease, acute critical illness) such that continued participation in the study may incur risk will also be discontinued.
- Significant symptoms of GH excess felt to be related to the study drug
- IGF-1 level that remains ≥ 3 standard deviations above the mean following a dose adjustment
- Development or worsening of retinopathy
- Clinical conditions, which in the best judgment of the investigator are believed to be harmful or potentially life-threatening to the participant, even if not felt to be related to the study drug and/or not addressed in the AE management section of the protocol.
- Request by participant to terminate study product(s)/intervention(s)

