With regard to injection site reactions, subjects will be informed to notify a study investigator of any sign of erythema, swelling, or pruritis. Subjects will also be informed of theoretical risks associated with excess GH, including arthralgia, paresthesia, and hyperglycemia, although these were not seen frequently in previous studies of GHRH¹⁻⁴⁴. In previous studies, there was no net effect of tesamorelin on glucose tolerance after 1 year of administration. Although there is a theoretical risk of neoplasm with an agent that increases GH and IGF-I, there is no evidence of increased malignancy with GHRH¹⁻⁴⁴. This risk is further minimized based on the data from previous studies showing achievement of physiologic, rather than pharmacologic, increases in IGF-1 SD scores. Nonetheless, subjects with active malignancy will be excluded from the study. For potential participants with previous malignancy that has been treated and cured, their health care providers will be contacted to discuss history and risk of recurrence. The study investigators, potential participant, and participants' providers will work together to weigh the potential benefits of the study drug against the risk of recurrence; only if an agreement is reached that participation poses no increased risk of recurrence will subjects with previous history of cured malignancy be enrolled.

IGF-1 Z-score ≥ 3 for subjects on tesamorelin will prompt a dose-decrease. IGF-1 levels will be monitored by an endocrinologist not otherwise involved in the study in order to maintain blinding of study physicians and study staff. This endocrinologist will know the study drug assignment. If a subject receiving tesamorelin has an IGF-1 Z-score ≥ 3 (i.e., an IGF-1 level of 3 SD or more above the mean for age and gender), then the endocrinologist will contact the site investigator to request a dose decrease to 1mg. If the subject is in the double-blind portion of the study (first 12 months), a dummy dose decrease will also be requested for a placebo patient seen at the same site during the same time-frame in order to maintain blinding. If the IGF-1 Z-score for the

tesamorelin subject remains ≥ 3 at the next visit, tesamorelin administration will be discontinued but the subject will continue to be followed for safety.

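### Sections 11.1.1 and 14.4.1 take a tesamorelin subject with persistently high IGF-1 off the study, and no section secures that subject's month-12 assessments, so outcome data can be lost in one arm only

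*Combined protocol and SAP*

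**What the plan says.** The event at issue is an IGF-1 z-score that is still 3 or more after the step down to 1 mg.

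- **14.4.1** (tesamorelin subjects): "following dose reduction, the subject will be discontinued from the study".
- **11.1.1** gives the same outcome: "s/he will be discontinued from the study. If the next IGF-1 z-score is". The second sentence of that quote goes on to keep subjects whose level has fallen below 3.
- **14.3.1** is the list of "criteria for permanent discontinuation of further study intervention for an individual participant". It includes an IGF-1 level still at least 3 "standard deviations above the mean following a dose adjustment".
- **14.3.2** is a separate list, introduced by "The criteria for premature discontinuation from the study for an individual participant are". It has no IGF-1 item.
- **18.4.4** says that if the z-score remains high "at the next visit, tesamorelin administration will be discontinued but the subject will continue to be followed for safety".

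For anyone who leaves early, 12.4.8 says: "Subjects who leave the study early will be asked to come for an early termination visit in lieu of their next scheduled study visit". In Appendix A that visit includes MRS, AST, ALT, GGT, FibroScan, lipids and fasting glucose. It has no biopsy, no frozen serum and no isotope or clamp study.

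A matched placebo subject receives a dummy dose reduction (14.4.1, 18.4.4). No dummy discontinuation is described. Section 15.8.4 specifies intention to treat with all available data.

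**The concern.** Followed as written, 11.1.1 and 14.4.1 remove subjects from outcome assessment in the tesamorelin arm only. Those removed are picked out by a pharmacodynamic response to tesamorelin. An intention-to-treat analysis is meant to avoid that kind of post-randomisation selection.

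The endpoints are not equally exposed. Liver fat has interim scans that the mixed model can use. Histology and de novo lipogenesis are measured only at baseline and 1 year and compared as changes (15.8.4), so a subject without the later value drops out of the comparison. CK-18 also has no serum sample between baseline and month 12.

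The plan expects missing data to be at random (15.8.4). Here the missingness would be driven by IGF-1, which is not a term in the stated mixed model.

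**Working it through.** **1. What each section secures at month 12**

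| Section | Drug | Study status | Month-12 MRS, biopsy, CK-18 |
|---|---|---|---|
| 11.1.1, 14.4.1 | stopped | off study | not collected unless the early termination visit happens to fall at month 12, and then MRS only |
| 14.3.1 | stopped | not stated | not stated |
| 18.4.4 | stopped | followed for safety | not stated |

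**2. Which visit patterns lose data, on the off-study rule**

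On-drug IGF-1 draws in the double-blind phase are at months 0.5, 3, 6, 9 and 12 (12.1.6, Appendix A). A reduction is due within 1 month of the draw (14.4.1). I assume that the recheck result is acted on before the next visit and that the early termination visit takes that visit's place.

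| First high | Reduced by | Recheck | Visit replaced | Month-12 MRS | Month-12 biopsy, CK-18, isotope/clamp |
|---|---|---|---|---|---|
| 0.5 | 1.5 | 3 | 6 | lost | lost |
| 3 | 4 | 6 | 9 | lost | lost |
| 6 | 7 | 9 | 12 | done at termination visit | lost |
| 9 | 10 | 12 | none before month 12 | done | done |

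Month-12 MRS is lost in 2 of 4 patterns, and the biopsy and associated samples in 3 of 4. These are counts of patterns, not probabilities. In both patterns that lose month-12 MRS, a scan at about month 6 or later still exists.

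**3. Endpoints in 8.5 against the early termination visit**

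(a) ALT, AST and GGT are collected. (b) Histology, (c) CK-18, (d) endogenous glucose production and (e) de novo lipogenesis are not; (d) and (e) are MGH only. That is 4 of 5. The longer list in 15.2.2 also has elastography, lipids and fasting glucose, which that visit does collect.

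**4. The plan's own power figures**

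Inputs from 15.4: 60 randomised, 20% discontinuation, so 60 × 0.8 = 48 evaluable, or 24 per arm; alpha 0.05 (taken as two-sided, which reproduces the stated power). Two-sample t-test: noncentrality = d / √(1/n₁ + 1/n₂), with n₁ + n₂ − 2 degrees of freedom.

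- Primary: d = 9.4/11 = 0.855; noncentrality 0.855/√(2/24) = 2.96; power 82.6% (stated 82%). With 45 evaluable, 80.0% (stated 80%).
- Secondary: d = 0.89; noncentrality 0.89/√(2/24) = 3.08; power 85.5% (stated 85%).

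**5. Cost of one-arm loss**

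No rate of persistent elevation is given, so I assume 1 to 3 further losses, tesamorelin arm only.

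| Tesamorelin v placebo | Secondary, 0.89 SD | Primary, if those subjects gave no MRS data |
|---|---|---|
| 24 v 24 | 85.5% | 82.6% |
| 23 v 24 | 84.7% | 81.7% |
| 22 v 24 | 83.9% | 80.8% |
| 21 v 24 | 82.9% | 79.8% |

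The last column is a worst case, because interim scans are used. The 0.89 SD figure covers variables collected at both sites, so it does not describe (d) and (e).

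**6. Possible shift in a completers' comparison**

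If k of 24 tesamorelin subjects are lost and their mean change differs from the rest by D, the arm mean shifts by (k/24) × D. Assuming D of 0.5 to 1 SD, one loss shifts it by 0.02 to 0.04 SD and three by 0.06 to 0.125 SD, against a design effect of 0.89 SD. The documents do not fix the direction.

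**The case against.** **The sections may not conflict.** A reader might infer from 14.3.1 and 14.3.2 that the protocol keeps these subjects in the study, so that 11.1.1 and 14.4.1 are contradicted outright. The documents do not support that. Pregnancy is also listed in 14.3.1 and absent from 14.3.2, yet 14.2 says "Withdraw from the study but continue in follow-up for safety". Listing in 14.3.1 is therefore compatible with leaving the study, and 18.4.4 can be read as off-study safety follow-up of the same kind. This objection stands. What survives it is that no reading brings the subject back for month-12 outcomes.

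**The plan already responds to unequal dropout.** Section 15.8.4 provides for sensitivity analyses if dropout is higher than expected or differs between groups, with last observation carried forward and multiple imputation considered. This stands as mitigation, but it cannot recover a biopsy or serum sample that was never taken.

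**The allowance may cover it.** The 24 per arm already assumes that 6 of 30 are lost. Nothing shows that IGF-1 stops would come on top, so the power losses above are upper illustrations. Section 18.4.4 also describes IGF-1 increases in earlier studies as physiologic, and the trigger needs persistence after the dose is halved.

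**Other stops have the same split in wording.** Malignancy (14.3.1, 14.4.6) and injection-site reaction (14.3.1, 14.4.2) do too. Injection-site erythema was commoner on drug in the phase III studies (8.5% v 2.7%, 18.4.4), though that is not the stopping threshold. Either arm can meet those rules; the IGF-1 rule is confined to tesamorelin subjects.

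**Conclusion.** The point holds as a modest design weakness. Two sections take these subjects off the study, the others leave their status open, and none secures month-12 data. Any loss falls in the tesamorelin arm alone and is selected by response to the drug.

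The size is probably small. On the assumed 1 to 3 extra losses, power falls by roughly 1 percentage point per subject, and less if the 20% allowance absorbs them. The primary endpoint is the least exposed, because interim and early-termination scans can enter the mixed model. Histology and CK-18, and at MGH the isotope and clamp measures, are the most exposed. A reader might infer that the primary result or the trial's power is seriously threatened. The documents give no trigger rate that would support this.

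The conclusion rests on 11.1.1 and 14.4.1 being followed literally and on the rule being met before the month-12 visit. It is worth correcting because the correction is cheap.

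**What to change.** In 11.1.1 and 14.4.1, for this trigger only, replace the words that remove the subject from the study with:

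*Study drug is permanently discontinued. The subject remains in the study and is asked to complete the remaining double-blind visits, including the month-12 MRS and laboratory tests and, if the subject agrees, the month-12 biopsy and (MGH) isotope and clamp study.*

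Align 18.4.4 with this. Keep the trigger as it is: tesamorelin subjects, next scheduled IGF-1 after dose reduction. Do not widen it to any later sample. That would change a safety stopping rule and could force a permanent stop on a sample drawn a day after the reduction. In 15.8.4, exclude subjects off drug from the 12-versus-18-month comparison of continued treatment.

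**Cost.** A short text change in these sections and no assessments beyond those already scheduled. Safety protection is unchanged, since drug stops at the same point. Some month-12 values will come from subjects off drug and may dilute the on-treatment effect, which intention to treat accepts. A drug stop has no placebo dummy, so site staff may infer assignment. That happens under any reading, but these subjects would now be seen at later visits. Central reading of MRS (12.3.1) and histology (12.3.3) limits the effect on those outcomes.

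### Sections 14.3.1 and 14.4.2 give incompatible instructions for a first, non-systemic injection-site reaction with erythema and pruritis beyond 3 cm: permanent stop versus hold and one optional restart

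*Combined protocol and SAP*

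**What the plan says.** Section 14.3.1 introduces its list with "The criteria for permanent discontinuation of further study intervention for an individual participant are". One item is erythema and/or pruritis reaching at least 3 cm "beyond the immediate injection site, indicating allergic reaction". The item makes no distinction between a first and a repeat reaction, sets no condition about systemic symptoms, and does not mention rechallenge.

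Section 14.4 is introduced as guidance for known side effects that do not call for stopping drug at once. Within it, 14.4.2 asks subjects with a mild local reaction to "let the study investigator know of any spread beyond the injection site or any pruritis, either of which may represent hypersensitivity". It then states: "Erythema and pruritis extending >3cm beyond the injection site will be treated as a likely hypersensitivity reaction". If systemic symptoms accompany the reaction, the subject is stopped immediately and sent for care. If not, "subjects will be asked to hold the study drug until resolution of the symptoms". After that, at the investigator's discretion, "the subject may restart study drug once to determine if the reaction recurs". The last step is: "With recurrence, subjects will be discontinued from the study".

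Neither section refers to the other.

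**The concern.** The same first reaction draws a mandatory permanent stop from one section and a permitted restart from the other. The restart re-exposes a subject after what the protocol itself regards as probable hypersensitivity. Known hypersensitivity to tesamorelin or mannitol is an exclusion criterion (10.1.2). Dosing is at home apart from observed administration at the baseline and 12-month visits (18.4.4), and 14.4.2 does not require the restart to be supervised.

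There is also a compliance question. Section 13.2.1 counts any departure from approved procedures as a deviation. Deviations that raise the risk of harm go to the MGH IRB within 7 calendar days (13.2.4), and serious deviations go to the NIAID IRB within 7 calendar days (13.2.3). An investigator who restarts under 14.4.2 cannot tell from the protocol whether that is a deviation from 14.3.1, and the two sites could answer differently.

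**Working it through.** The point involves no sample size, power or error-rate figure, so the check is to apply each section's trigger and action to the same cases.

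| Case | 14.3.1 (and/or, at least 3 cm) | 14.4.2 (and, more than 3 cm) |
|---|---|---|
| Both signs, more than 3 cm, first time, no systemic symptoms | Permanent stop | Hold; one optional restart |
| Both signs, more than 3 cm, with systemic symptoms | Permanent stop | Immediate stop |
| Recurrence after a restart | Permanent stop, already due at the first reaction | Stop |
| One sign only, more than 3 cm | Permanent stop | Report it; no hold or restart route |
| Both signs, exactly 3 cm | Permanent stop | Trigger not met |

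1. **The conflict.** In the first row, more than 3 cm satisfies at least 3 cm, and two signs satisfy *and/or*. On its wording, 14.3.1 therefore covers every reaction that 14.4.2 allows to be restarted. A permanent stop and a restart cannot both be carried out.

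2. **The trigger mismatch.** Comparing the first and fourth rows, the reaction with one sign has only a stop rule, while the reaction with both signs has a route back to drug. That ordering runs against severity. It does not leave single-sign reactions without a rule, because 14.3.1 supplies one.

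3. **Whether 14.3.1 leaves second steps to 14.4.** Its other items suggest not. The glucose item requires confirmation by a repeat draw, matching 14.4.5. The IGF-1 item applies only if the level stays high after a dose adjustment, matching 14.4.1. The injection-site item has no second step.

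4. **Whether any text sets precedence.** None was found. The introduction to 14.4 sharpens the conflict, because it places this reaction among those not needing an immediate stop while 14.3.1 lists it as a reason for a permanent one.

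**The case against.** The best defence is that 14.4.2 is the working detail of the 14.3.1 item. Glucose, IGF-1 and malignancy also appear in both places, so 14.4 often elaborates 14.3.1. The 14.3.1 item speaks of a reaction that indicates allergy, whereas 14.4.2 speaks only of likely hypersensitivity and uses the restart as a test. On that reading drug is stopped for good only once allergy is confirmed. This may well be what was intended, but the text does not carry it. The allergy phrase reads more naturally as what a 3 cm extent signifies than as a further condition. Where 14.3.1 wants confirmation it says so, and the triggers do not match.

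Several limits on the point do stand. Restart is discretionary, comes only after resolution, and is not open to subjects with systemic symptoms. An investigator who stops and does not restart satisfies both sections. Section 18.4.4 reports that most side effects in the earlier Phase III studies were mild.

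A reader might also infer that because 14.4.2 removes subjects from the study, while 14.3.1 stops only the intervention, subjects with systemic or recurrent reactions would be lost to follow-up. The documents do not support this as a feature of 14.4.2. The wording is loose across the protocol: for persistently high IGF-1, 11.1.1 and 14.4.1 remove the subject from the study while 18.4.4 keeps the subject in safety follow-up, and 14.4.6 uses study removal for malignancy. Section 12.4.5 requests a termination visit, and 13.2.5 follows adverse events to their outcome or the end of follow-up.

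**Conclusion.** The inconsistency is real on the wording alone and should be corrected, because it concerns rechallenge after a likely hypersensitivity reaction. It is confined to first, non-systemic reactions with both signs beyond 3 cm, together with the mismatch in triggers. The conclusion assumes that the allergy phrase in 14.3.1 describes the reaction and does not add a confirmation step.

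Few subjects are likely to be affected. A reader might try to derive a count from the injection-site rates in 18.4.4, but those rates come without extent, without the share showing both signs, and without the share free of systemic symptoms. Any figure would rest on an arbitrary assumed fraction.

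A reader might also infer a threat to the primary result. Little effect is expected: the analysis is by intention to treat with all available data (15.8.4), and the sample size already allows for 20% to 25% discontinuation (15.4).

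**What to change.** Use one trigger in both sections (erythema and/or pruritis, at least 3 cm), add a cross-reference in each direction, and state one rule.

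- **Option (a), no rechallenge.** Leave the 14.3.1 item as it is. In 14.4.2, replace the hold, restart and recurrence sentences with: *Study drug will be permanently discontinued (see 14.3.1).* Keep the direction to immediate care for systemic symptoms. Stopping without restart is the only course that complies with both sections as now written. The cost is the option of rechallenge, so some subjects whose reaction would not have recurred will stop drug.
- **Option (b), keep rechallenge.** Rewrite the 14.3.1 item along these lines: *Erythema and/or pruritis reaching 3 cm or more past the injection site, if accompanied by systemic symptoms, not rechallenged, or recurring after the single restart allowed in 14.4.2.* The cost is a slight loosening for single-sign reactions, which 14.3.1 now stops outright.

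Whether to allow rechallenge is a clinical decision for the sponsor. Either option changes only a few sentences and leaves visits, sample size and analysis untouched.
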